4.5 Safety Endpoints

The safety assessments to evaluate the overall safety of MDNA55-05 will include:

- Serious adverse events (SAEs) and treatment emergent adverse events (TEAEs);
- Vital signs;
- Physical examinations;
- Neurological examinations;
- Electrocardiogram (ECG);
- Clinical laboratory results (haematology, serum chemistry, coagulation, urinalysis);
- Karnofsky Performance Status (KPS).

4.6 Other Endpoints

- MDNA55 PK parameters in peripheral plasma;
- Anti-MDNA55 antibody (ADA) titer in serum;
- Neutralizing antibody (NAb) titer (if anti-MDNA55 titer is observed).

5. STUDY POPULATIONS

5.1 Intent to Treat Population (ITT)/Safety

An ITT population will comprise all subjects who sign the ICF and who receive any amount of study drug.

5.2 Modified Intent to Treat Population (mITT)

A modified ITT population for secondary response analyses (mITT) will comprise all subjects who receive any amount of study drug and have adequate imaging (at least 1 post-treatment scan) and clinical data for the ORR analysis.

5.3 Per Protocol Population (PP)

The PP population will comprise all subjects in the mITT population who also have no major protocol violations during the study. Efficacy analyses will be conducted on this population in support of the primary efficacy results.

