9.2.2.1 Intent to Treat (ITT)

An ITT population will comprise all subjects who receive any amount of study drug will be used for the primary efficacy analyses, other purely survival-based endpoints and all safety analyses.

A modified ITT population for secondary imaging-based analyses, including PFS, (mITT, see below) will comprise all subjects who receive any amount of study drug and have adequate imaging or clinical data for the ORR analysis. NOTE: Patients who expire or progress clinically prior to the first MRI examination will not be evaluable for any of the response assessments.

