9.2.2.2 Per Protocol (PP) Population

The PP population will comprise all patients in the ITT population (or mITT for imaging-based endpoints) who also have no major protocol violations during the study. This population will be finalized prior to the final lock and primary analysis of the study data. Efficacy analyses will be conducted on this population in support of the primary efficacy results.

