6. STATISTICAL ANALYSIS CONSIDERATIONS

6.1 Handling of Missing Data and Dropout

All available data will be used, and no efficacy data will be imputed. For the analyses of response, subjects with baseline assessments but no post-treatment assessments will be non-evaluable. For time to event variables, subjects not known to have experienced an event at the time of analysis will be censored.

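### The SAP draws the supportive per-protocol set for overall survival from the imaging-based mITT set, contrary to protocol 9.2.2.2, and so can drop early deaths from that analysis

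*SAP*

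**What the plan says.** The documents give two rules for the per-protocol set.

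- **SAP 5.3:** "The PP population will comprise all subjects in the mITT population who also have no major protocol violations during the study". It adds: "Efficacy analyses will be conducted on this population in support of the primary efficacy results". SAP 4.1 makes OS the only primary endpoint.
- **Protocol synopsis:** the same mITT-based rule as the SAP.
- **Protocol 9.2.2.2:** "The PP population will comprise all patients in the ITT population (or mITT for imaging-based endpoints) who also have no major protocol violations".

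Entry to mITT depends on imaging. SAP 5.2 describes mITT as a set for the secondary response analyses and requires that subjects "have adequate imaging (at least 1 post-treatment scan) and clinical data for the ORR analysis". The protocol (synopsis and 9.2.2.1) is looser, asking for adequate imaging or clinical data, but 9.2.2.1 notes: "Patients who expire or progress clinically prior to the first MRI examination will not be evaluable for any of the response assessments". SAP 6.1 says of the response analyses that "subjects with baseline assessments but no post-treatment assessments will be non-evaluable".

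The primary OS analysis is on ITT, meaning all subjects who received any study drug (protocol synopsis, section 9 and 9.2.2.1). Protocol 9.2.2.1 also assigns the other purely survival-based endpoints to ITT.

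**The concern.** OS needs no scan. Drawing the PP set for OS from a set that requires a scan makes membership depend on living long enough to be scanned. The subjects lost this way include those with the shortest survival, and they are lost for a reason unrelated to protocol compliance.

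The study has no control arm, and OS is judged against a fixed median of 8 months, so nothing offsets this selection. The purpose of a PP analysis is to show whether the ITT result stands up among compliant subjects. Here PP survival could exceed ITT survival even with an inactive drug, and the better figure could be read as confirmation.

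**Working it through.** **1. Where a compliant subject who dies before Day 30 is counted**

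| Rule | ITT (primary OS) | PP analysis of OS |
|---|---|---|
| Protocol 9.2.2.2 | counted as a death | counted as a death |
| SAP 5.3 with 5.2, qualifying scan = Day 30 response MRI | counted as a death | dropped |
| SAP 5.3 with 5.2, qualifying scan = MRI 18-30 h after infusion | counted as a death | normally counted |

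SAP 5.2 does not name the scan. Protocol Table 6 gives tumor response assessment as a purpose only for the follow-up MRIs, which start at Day 30 (±3).

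**2. The plan's own figure**

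Inputs from protocol 9.1: 46 subjects, exponential survival, median 8 against 11.5 months, one-sided 10%, 12 months' follow-up, uniform accrual. The accrual length A is not given and is assumed. With λ = ln2/median:

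- P(event) = 1 − [exp(−12λ) − exp(−(12+A)λ)]/(λA), and d = 46 × P(event)
- power = Φ{[ln(λ0/λ1) − 1.2816/√d0] × √d1}

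For A = 18 months, d0 = 37.8 and d1 = 32.4. Power = Φ[(0.3629 − 0.2085) × 5.69] = Φ(0.88) = 0.81. For A = 12 and 24 months it is 0.793 and 0.822. The stated power of over 80% is reproduced, approximately, if accrual takes about 12 months or more. The same model is used below.

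**3. Size under a constant hazard**

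λ0 = 0.6931/8 = 0.0866 per month, and Day 30 = 30/30.44 = 0.986 month.

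- P(death before Day 30) = 1 − exp(−0.0866 × 0.986) = 0.082, or 3.8 of 46.
- An exponential distribution has no memory, so the median among survivors to Day 30 is 8 + 0.99 = 8.99 months. The shift is 0.99/3.5 = 28% of the planned gain.
- Six-month OS moves from 59.5% to 0.595/0.918 = 64.8%, and 12-month OS from 35.4% to 38.5%.
- With the scan at Day 27 or Day 33, the median is 8.89 or 9.08 months.

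**4. Size if early deaths are rarer**

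Let the hazard in the first 12 weeks (2.76 months) be a fraction f of the later hazard h, with the overall median held at 8 months: h = 0.6931/(2.76f + 5.24). The median shift from removing deaths before Day 30 is f × 0.986 month.

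| f | Deaths before Day 30, of 46 | Median after removal (months) | Shift (months) |
|---|---|---|---|
| 1 | 3.8 | 8.99 | 0.99 |
| 0.5 | 2.3 | 8.49 | 0.49 |
| 0.25 | 1.3 | 8.25 | 0.25 |
| 0 | 0 | 8.00 | 0 |

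If a scan about one day after treatment qualifies, the expected loss is about 0.1 of 46, even with f = 1.

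**5. What the protocol's test would do on that set (hypothetical)**

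Simulation: 40,000 trials, true median 8 months, 46 subjects, assumed accrual of 18 months, at least 12 months' follow-up, statistic (E − O)/√E against 1.2816. With all subjects it rejects in 8.9% of trials. With deaths before Day 30 removed it rejects in 21.9% (23.2%, 22.1% and 21.1% for accrual of 6, 12 and 24 months). The cause is simple: each of the 42.2 subjects retained on average adds 0.0866 × 0.986 = 0.085 expected deaths over a period in which none can be observed, about 3.6 in total.

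**The case against.** The strongest reply is that the SAP may not drop these subjects at all. It asks for one post-treatment scan, and each completed infusion is followed by an MRI within 4 hours and another at 18-30 hours. Table 6 gives tumor dimensions and volume among the purposes of the second. A subject who dies on Day 20 would normally have both. This reading is possible but the weaker one. SAP 5.2 wants imaging adequate for the response analysis, protocol 7.5.2.4 says the 18-30 hour scan is for non-specific enhancement, and the protocol's note on deaths before the first MRI would cover almost nobody if in-hospital scans counted. What stands is that the number dropped depends on a scan the SAP does not name.

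A second reply is that early deaths should be few. Eligibility requires a life expectancy of at least 12 weeks and a KPS of at least 70, and excludes mass effect and uncontrolled intracranial pressure. This stands, and it is why the constant-hazard result is the top of the Day 30 range in step 4 and not a forecast.

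Three stronger readings are tempting, and the documents do not support them:

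- **That the primary OS analysis is biased.** The protocol fixes it on ITT; PP is supportive only.
- **That the trial's error rate rises to about 22%.** Neither document plans a log-rank test on PP. SAP 7.7.1 lists Kaplan-Meier estimates and confidence intervals, with no PP decision rule.
- **That early clinical progressors are also removed.** The note naming them is in the protocol, concerns response assessments only, and is not carried into SAP 5.2. Such a subject may well have a scan at the early termination visit (protocol 7.5.4).

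**Conclusion.** The conflict holds. SAP 5.3 and the synopsis apply to OS an imaging condition that protocol 9.2.2.2 keeps for imaging-based endpoints. The damage is confined to the supportive PP analysis of OS.

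If the Day 30 MRI is the qualifying scan, removing the deaths before it can only push PP survival up. Under the null the median shift is between 0 and about 1 month: about 1 month with a constant hazard from Day 0, about 0.5 or 0.25 month if the early hazard is half or a quarter of the later one, and none if nobody dies early. If the 18-30 hour MRI qualifies, the effect is negligible. The documents do not settle the early hazard or the qualifying scan. The contradiction between the rules depends on neither.

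**What to change.** In SAP 5.3 and the protocol synopsis, adopt the rule of protocol 9.2.2.2. For OS and other survival-only endpoints, PP is the ITT subjects with no major protocol violation. For imaging-based endpoints only, PP is the mITT subjects with no major protocol violation. Make the change before database lock.

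Naming the qualifying scan in SAP 5.2 would also remove the ambiguity for the imaging-based analyses, but the OS problem is solved without it.

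The cost is one sentence in each place and no new data. The PP estimate of OS may come out slightly less favourable.

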5.4 IL4R Population

The IL4R analysis population will be those in the ITT population who have archived tissue or adequate tissue available for analysis and will be used for efficacy analyses in subgroups according to IL4R expression status.

5.5 PK Population

The PK Population may include all subjects who received any dose of MDNA55 and who had at least one post-treatment PK sample available. Subjects who received the highest dose concentrations (6 and 9 ug/mL) will be analysed first. If all results from this cohort are Below Level of Quantitation (BLQ), consistent with historical data showing no evidence of systemic exposure with MDNA55, no further subjects will be analysed unless requested by a regulatory authority.

5.6 Anti-Drug-Antibody Population

The ADA Population will include all subjects who received any dose of MDNA55 and who had a baseline (pre-treatment) and at least one post-treatment ADA sample available.

Neutralizing antibody titers will be assessed in the ADA population as appropriate and applicable.

6. STATISTICAL ANALYSIS CONSIDERATIONS

6.1 Handling of Missing Data and Dropout

All available data will be used, and no efficacy data will be imputed. For the analyses of response, subjects with baseline assessments but no post-treatment assessments will be non-evaluable. For time to event variables, subjects not known to have experienced an event at the time of analysis will be censored.

6.2 Handling of Missing or Incomplete Date

To handle missing or partial AE and concomitant medication dates, the following rules will be applied.

For partial start dates:

- 1. If the month is unknown, then:
 - a) If the year matches the year of the dose date, then impute the month and day of the dose date.
 - b) Otherwise, assign "January."
- 2. If the day is unknown, then:
 - a) If the month and year match the month and year of the first dose date, then impute the day of the dose date.
 - b) Otherwise, assign "01."

For partial end dates:

- 1. If the month is unknown, then assign "December."
- 2. If the day is unknown, then assign the last day of the month.

After implementing the rules above, to determine whether AEs (or medications) with missing start or stop dates are pretreatment or on/after treatment, the following strategy will be used:

- 1. If the start date and stop date are both missing, then the most conservative approach is taken and the AE (or medication) is treatment emergent (or concomitant medication).
- 2. If the start date is missing but the stop date is not missing and is on or after the day of catheter placement, then the most conservative approach is taken and the AE (or medication) is treatment emergent (or concomitant medication).
- 3. If the start date is missing but the stop date is not missing and is before catheter placement and after the date of signed informed consent, then the medication is before treatment (or prior medication). Note: this is not applicable to AEs as all AE collection start from date/time of catheter placement.
- 4. If the start date is not missing but the stop date is missing, then the most conservative approach is taken, and medication concomitant while the AE is defined by start date.

6.3 Visit Windowing

Not applicable for this study.

6.4 Baseline Definition

The baseline value is defined as the last non missing assessment prior to catheter placement.

6.5 Derived Variables

Change from Baseline is defined as Post baseline value – Baseline value.

Percent Change from Baseline is defined as the (Post baseline value – Baseline value/ Baseline value) *100.

Study day is defined as the number of days from the date of catheter placement:

Study Day = (Target Date - Date of catheter placement) + 1 if target date is greater than or equal to the date of catheter placement.

or

Study Day = (Target Date – Date of catheter placement) if target date is less than date of catheter placement.

7. STATISTICAL METHODOLOGIES AND ANALYSES

7.1 General Statistical Conventions

All statistical analysis will be performed using SAS® version 9.3 or above. Summary tables (descriptive statistics and/or frequency tables) will be provided for baseline variables, efficacy variables and safety variables. Continuous variables will be described by descriptive statistics (n, mean, standard deviation, minimum, maximum, median. Frequency counts and percentage of subjects within each category will be provided for categorical data. Summaries will be provided for overall treatment.

Decimal Precision Convention: Means and medians will be reported to one decimal place more than the raw data. Standard deviation will be reported to two more decimal places than the raw value. The minimum and maximum will be reported to the same decimal as the raw data. In case of n<2, where n indicates the number of evaluable subjects at the particular time point, only n, mean, minimum and maximum will be displayed. The statistic "Missing" will also be evaluated by enumerating the number of missing entries/subjects, if any at that visit, and presented as a summary statistic only for the resulting time points.

Categorical variables will be summarized using the frequency count and the percentage of subjects in each category. All percentages will be rounded to one decimal point. The number and percentage of subjects will always be presented in the form XX (XX.X). To ensure completeness, all summaries for categorical and discrete variables will include all categories, even if none of the subjects are in that category. Counts of zero in any category will be presented as "0". Unless otherwise noted, for all percentages, the number of subjects in the analysis population for the treatment group will be the denominator.

7.2 Subject Disposition

Subject disposition information will be summarized according to the following:

- number of subjects who are enrolled:
 - o overall
 - o according to MDNA55 concentration (1.5, 3, 6, and 9 µg/mL)
 - o according to protocol version
- number and percent of subjects who completed the 360 day study visit
- number of screen failure subjects
- number of subjects who are treated

In addition, the number of treated subjects who discontinued from the study, and the reasons for discontinuing from the study will also be summarized. In the summary table, percentages will be calculated using the number of enrolled subjects as the denominator. All the population counts and percentages will be displayed in the summary.

Subject disposition data will be listed including dose (concentration, volume and total dose), enrollment date (consent date), protocol version consented under, infusion start date/time, infusion end/date and time, the withdrawal/completion date, and reason for withdrawal.

7.3 Protocol Deviations

Major protocol deviations will be summarized by deviation category. This analysis will be performed for all subjects. All protocol deviations will be listed by subject.

7.4 Demographics and Baseline Characteristics

Demographic and baseline Subject characteristics will be summarized based on the ITT population and according to the following categories:

- Overall:
- By concentration of MDNA55 administered (1.5, 3, 6, 9 μg/mL);
- By low and high total dose of MDNA55 administered (based on median);
- By IL4R status (IL4R^{High}, IL4R^{Low}).

All demographic and other baseline characteristics will be provided in a listing for ITT Population. Categorical variables will be summarized using frequencies while continuous variables will be summarized using mean, SD, median, minimum, and maximum.

7.4.1 Demographics

The following demographic characteristics will be summarized

- Age (years)
- Sex
- Ethnicity
- Race

Age will be calculated as: age = Integer \leq [(ICF date – Date of Birth + 1) / 365.25]

7.4.2 Baseline and Disease Characteristics

The following baseline characteristics of the underlying disease will be summarized:

- Karnofsky Performance Score.
- MGMT Status (positive/methylated or negative/unmethylated)
- Steroid use (Yes, No).
- GBM grade
- Diagnostic method of Glioblastoma (CT, MRI, Biopsy).
- Prior Glioblastoma treatment (Surgery, Radiotherapy, Temozolomide, Other Chemotherapy, Investigational, Other).
- Initial diagnosis to 1st relapse (months)
- Initial diagnosis to current relapse (months)
- Initial diagnosis to start of MDNA55 treatment (months)
- Number of prior relapses (1 or 2)
- Max tumor diameter at baseline (cm)
- Tumor volume at baseline (cm3)

- Lymphocyte count
- Height (cm)
- Weight (kg)
- Body mass index (BMI)

7.5 Medical History

Medical history will be summarized by the number and percentage of subjects in each system organ class (SOC), preferred term (PT), and overall using the safety population. Subjects will be counted only once at the preferred term (PT), only once at the system organ class (SOC), and only once at subject level for the counting of total number of subjects with a medical history term. Counts will be presented in descending frequency of SOC term for the treatment column unless otherwise specified. Medical and surgical history will be coded using Medical Dictionary for Regulatory Activities (MedDRA) latest version.

Listings of Medical History will be provided for using the Safety Population.

7.6 Prior and Concomitant Medications/ Corticosteroids

Prior and concomitant medications will be coded using World Health Organization-Drug Dictionary and will be categorized by preferred name and ATC level 4 class per WHO, which will be summarized using the Safety Population for each of the 3 periods: prior to catheter placement, during infusion and post end of infusion. Listings of all prior and concomitant medications will be provided for using the Safety Population.

Prior Medications/Corticosteroid: Prior medications will include any medication having a stop date/time prior to catheter placement.

Concomitant Medications/Corticosteroid: Concomitant medications, are any medications having a stop date/time after catheter placement or ongoing.

All concomitant medications/corticosteroids will be reconciled accordingly at point of subject early withdrawal /or study completion as either having a stop date or ongoing.

7.7 Efficacy Analyses

7.7.1 Primary Efficacy Analyses

The primary efficacy assessment will be overall survival defined as the date of catheter placement until death from any cause. Subjects who are not known to have died at the time of the analysis will be censored at the date of last contact.

OS= Date of death/Censored – Date of catheter placement +1.

Survival rates at 6, 9, and 12 months and their exact 95% CI for the primary endpoint (OS) along with the estimate for median and its 80%, 90% and 95% CI, will be produced using KM method. KM estimates of OS will also be presented graphically at 6, 9 and 12 months.

Same summaries will be produced for all subgroups and other time-to-event endpoints.

7.7.1.1 Subgroup Analyses

Subgroup analysis is planned for the primary endpoint OS to investigate whether treatment effect is consistent within the subgroups. Forest plots will be used to graphically represent the subgroup estimates and corresponding confidence intervals. All the subgroups are provided in a separate document attached in section 11 Appendices. Also, subgroup analysis is conditional upon availability of data.

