7.3.2 O6-Methylguanine-Methyltransferase Analysis

MGMT-expressing cancer cells (harboring unmethylated MGMT promoters and therefore resistant to temozolomide) are sensitive to MDNA55.

Thus, tumor tissue specimens from subjects will be processed at a CLIA certified laboratory for MGMT DNA methylation analysis using a quantitative methylation-specific PCR technique. Primary and secondary endpoints will be analyzed against the MGMT methylation status.

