3.2 Randomization and Blinding

This study is a single-arm design. All subjects will receive active treatment. No randomization will be performed. No blinding procedures are employed.

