4.3 Other Efficacy Endpoints

- Duration of response (DOR). Defined as the time from first response until disease
 progression (per RANO-based criteria and as determined by an independent central
 review) or death among those subjects achieving a complete response (CR) or partial
 response (PR) to treatment;
- Duration of clinical benefit (DOCB). Defined as the time from first response or disease stabilization until disease progression (per RANO-based criteria and as determined by an independent central review) or death among those subjects achieving tumor control: complete response (CR), partial response (PR), or stable disease (SD);
- To determine the Tumor Control Rate (TCR) defined as the proportion of subjects in whom the best overall response is determined as complete response (CR), partial response (PR) or stable disease (SD) based on different sets of imaging-based response criteria. Use of sub-therapeutic doses of Avastin will also be considered in determination of TCR (and will result in a variant of the TCR being calculated);
- Time to Tumor Progression (TTP). Defined as the time from treatment until tumor progression; does not include death.

4.4 Exploratory Endpoints:

 To determine the relationship between efficacy endpoints (i.e., OS, PFS, DOR, DOCB, TTP) and tumor response category using different sets of imaging-based response criteria;

- To determine the relationship between efficacy endpoints (i.e., OS, PFS, DOR, DOCB, TTP, TCR) and IL4R expression status;
- To determine the relationship between efficacy endpoints (i.e., OS, PFS, DOR, DOCB, TTP) and various prognostic factors (i.e., age, sex, KPS, MGMT status, etc);
- To determine the relationship between efficacy endpoints (i.e., OS, PFS, DOR, DOCB, TTP) and use of concomitant medication (i.e., Avastin, steroids);
- To determine the relationship between efficacy endpoints (i.e., OS, PFS, DOR, DOCB, TTP) and various treatment and drug distribution parameters (i.e., MDNA55 concentration, total dose, volume of infusion, percent tumor coverage, etc.);
- To assess the performance of Brainlab catheter during infusion through real time MRI monitoring;

Note: All exploratory analyses will be conditional upon data being available.

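### SAP 7.7.1.1 asks subgroup OS forest plots whether the treatment effect is consistent, but in a single-arm trial they show only the survival of treated subjects, in which prognosis and treatment effect cannot be separated

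*SAP*

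**What the plan says.** SAP 7.7.1.1 gives the subgroup analysis of OS a stated purpose: "to investigate whether treatment effect is consistent within the subgroups". The display follows: "Forest plots will be used to graphically represent the subgroup estimates and corresponding confidence intervals".

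SAP 7.7.1 says what is estimated. After describing survival rates at 6, 9 and 12 months "along with the estimate for median and its 80%, 90% and 95% CI, will be produced using KM method", it adds: "Same summaries will be produced for all subgroups and other time-to-event endpoints". Each subgroup therefore gets Kaplan-Meier rates and a median, as the whole group does.

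SAP 3.2 gives the design: "This study is a single-arm design. All subjects will receive active treatment. No randomization will be performed".

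Three other places bear on the point:
- SAP 4.4 lists as exploratory the relationship between efficacy endpoints and "various prognostic factors (i.e., age, sex, KPS, MGMT status, etc").
- Protocol 7.3.2 says: "Primary and secondary endpoints will be analyzed against the MGMT methylation status".
- Protocol 9 and 9.2.5.3 (and the synopsis) plan to examine the effect of treatment by IL4R level.

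The only outside OS reference is one median of 8 months for the whole population (Protocol 1.4, 9.1, 9.2.5.1). The subgroup list is in a document attached to SAP Section 11, which is not in the public text.

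**The concern.** A treatment effect is a contrast between treated and untreated outcome. To ask whether it is consistent across subgroups, one needs that contrast in each of them. Here each subgroup supplies only the treated half. The other half could come only from an external reference for the same subgroup, and the text available gives none.

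The stated purpose invites two unsupported conclusions in the study report. A subgroup with longer survival may be said to benefit more, when it would have lived longer anyway. Similar estimates or overlapping intervals may be reported as a consistent effect, when the subgroups are too small to show otherwise, or when a difference in prognosis and an opposite difference in effect have cancelled.

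**Working it through.** **The plan's own figures.** The plan gives no figure for subgroups. The inputs taken from it are the 46 evaluable subjects, the null median of 8 months and the alternative of 11.5 months (Protocol 9.1). Its stated power of over 80% for the primary test can be approximated. With 12 months of follow-up and an assumed 24 months of uniform accrual (the length is not stated), 34.2 deaths are expected under the alternative. On the log-rate scale, √34.2 × ln(11.5/8) − 1.282 = 5.848 × 0.3629 − 1.282 = 0.84, which gives power of about 80%. Shorter accrual gives less. The present point does not depend on this.

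**Step 1. What a subgroup estimate contains.** Let subgroup *g* have untreated hazard λ(g) and treatment hazard ratio θ(g). The treated hazard is λ(g) × θ(g), and the data inform only this product. The ratio between subgroups A and B is [λ(A)/λ(B)] × [θ(A)/θ(B)]: prognosis times effect modification. A ratio different from 1 does not imply that θ(A) differs from θ(B), and a ratio of 1 does not imply that they are equal.

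**Step 2. Same effect, different survival.** Assume exponential survival, two equal subgroups, and an untreated mixture with median 8 months. Then ½·exp(−8λ(A)) + ½·exp(−8λ(B)) = ½. With prognostic hazard ratio λ(A)/λ(B) = 0.5, put x = exp(−8λ(A)). The equation becomes x + x² = 1, so x = 0.618, λ(A) = 0.4812/8 = 0.0602, and the medians are 11.5 and 5.8 months. With no drug effect at all, the better subgroup reaches the design alternative of 11.5 months.

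Now give both subgroups the design effect, θ = 8/11.5 = 0.696:

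| Prognostic HR (assumed) | Medians, no drug effect | Medians, θ = 0.696 in both |
|---|---|---|
| 1/1.5 | 9.9 vs 6.6 | 14.2 vs 9.5 |
| 1/2 | 11.5 vs 5.8 | 16.6 vs 8.3 |

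The effect is identical in both subgroups, yet treated medians differ by 4.7 and 8.3 months.

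**Step 3. How often this would show.** Simulation with no drug effect, 23 subjects per side (46/2, assumed), mixture median 8 months, and censoring uniform between 12 and 24 months (assumed). The subgroup comparison is a two-sample log-rank test with |z| > 1.645. The test against 8 months is a one-sample log-rank, (O − E)/√E < −1.282, with E = (ln 2/8) × total follow-up time.

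| Prognostic HR (assumed) | Difference at two-sided 10% | Better subgroup beats 8 months at one-sided 10% |
|---|---|---|
| 0.7 | about 29% | about 27% |
| 0.6 | about 44% | about 40% |
| 0.5 | about 65% | about 56% |

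At hazard ratio 0.5 the two 95% confidence intervals for the exponential death rate overlap in about 78% of trials. Repeat runs move these figures by one or two points.

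**Step 4. The reverse case.** Let both subgroups have an untreated median of 8 months and let the drug work in only one, with 23 per side, 12 months of follow-up and an assumed 24 months of accrual. The Kaplan-Meier intervals for the two medians overlap as follows:

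| Treated medians | 95% intervals | 80% intervals |
|---|---|---|
| 8 vs 11.5 | 97% | 83% |
| 8 vs 16 | 86% | 55% |
| 8 vs 20 | 75% | 36% |

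Overlap is therefore common even when the effect is confined to one subgroup. How common depends strongly on which of the SAP's interval levels is drawn.

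**The case against.** The strongest reply is that this is one phrase in an exploratory subsection. SAP 4.4 speaks only of a relationship between factors and endpoints, Protocol 9.2.9 calls the IL4R tissue analysis descriptive, Protocol 7.3.2 makes no claim about treatment effect by MGMT, and the testing hierarchy in Protocol 9.4 does not name these subgroups. All of that is right, and it limits what could be claimed. It does not change the purpose written in SAP 7.7.1.1, which no sample size could serve without a control or a reference for each subgroup.

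The reply is also right about three stronger readings that a reader might infer:
- *That the SAP will test subgroups against each other or against 8 months, or read overlap as consistency.* The available SAP text plans neither test and states no reading rule. The percentages in Step 3 are not error rates of a planned procedure.
- *That the plots show prognosis.* They do not isolate it. A single arm can no more establish that a factor is purely prognostic than that it modifies the effect.
- *That MGMT or KPS subgroups of about 23 will be plotted without any reference.* The subgroup list is not in the public text, so the factors, the split and any subgroup references in it cannot be checked.

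**Conclusion.** The concern holds in this form: the purpose stated in SAP 7.7.1.1 cannot be met by the analysis it describes. The argument in Step 1 needs no numerical assumption. The sizes rest on exponential survival, an even split of 46, and assumed prognostic hazard ratios, censoring and accrual. Within those assumptions, prognosis alone would often look like a differing effect, and an effect confined to one subgroup would often leave overlapping intervals. The primary estimate, its test and the sample size are untouched. The matter should be corrected because it bears on what the study report may claim.

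**What to change.** 1. In SAP 7.7.1.1, replace the purpose with: *to describe OS by baseline subgroup among treated subjects*. State that no conclusion on consistency or difference of treatment effect will be drawn.
2. Add to the forest plot, for each factor, the between-subgroup hazard ratio with its confidence interval. Label it *OS difference among treated subjects (prognosis and treatment effect not separable)*, and not *prognostic*.
3. If any subgroup is set against a historical figure, use a prespecified reference for that subgroup, not the pooled 8 months.
4. Align the wording on treatment effect by IL4R level in Protocol 9 and 9.2.5.3, and in the synopsis.

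The cost is wording and one plot column, with no new data. The added hazard ratios will be imprecise: with 36 deaths split evenly, the standard error of the log hazard ratio is 2/√36 = 0.33, so a 95% interval runs from the estimate divided by 1.9 to the estimate times 1.9. The trial gives up a claim that its design cannot support.
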